# 1.0 PROTOCOL SUMMARY AND/OR SCHEMA

[figure not shown]
Title:	A Randomized Controlled Trial of Early, Upfront Palliative Radiation versus
	Standard of Care for Highest Risk Asymptomatic or Minimally Symptomatic
	Bone Metastases
Hypothesis:	Upfront, early palliative radiation of the highest risk asymptomatic or
	minimally symptomatic (non-opioid dependent) bone metastases in patients
	will lead to fewer skeletal-related events (SREs), defined as pathological
	fractures, spinal cord compression, or palliative radiotherapy or orthopedic
	surgery to bone.
Objectives:	Primary Objective:
	To assess whether early palliative radiation of the highest risk asymptomatic/minimally symptomatic bone metastasis in patients with metastatic cancer can decrease the number of SREs, defined as pathological fractures, spinal cord compression, or palliative radiotherapy or orthopedic surgery for bone metastases.
	Secondary Objectives:
	
 
To compare the number of hospitalizations related to SREs between standard of care and upfront RT arms
 

	
 
To compare pain-related quality of life of between standard of care and RT arms, using the Brief Pain Inventory (BPI) form
 

	
 
To collect health care utilities in the standard of care and RT arms using the EuroQol Group EQ-5D-5L form
 

	
 
To compare pain-free survival (PFS) and overall survival (OS) between RT and standard of care arms.
 

	
 
To evaluate CTCAE v4 toxicity events in the upfront RT arms.
 

Patient Population:	Patients with metastatic solid tumors of metastatic disease.
Design:	Randomized, prospective trial.
Treatment	In this trial patients will be divided into 2 cohorts. Patients in Cohort 1 will
Plan:	undergo standard of care therapy for bone metastases. Patients in Cohort 2 will undergo upfront RT to ≤5 highest risk bone metastases first followed by standard of care therapy.
Number of	We plan to recruit 74 patients (see details of eligibility in the biostatistics
Patients:	section) to this protocol over 2 years.

Page **5** of **30** Version: 2/26/16

# PROTOCOL SCHEMA

# **PATIENT POPULATION**

- Patients with metastatic high risk bone metastasis defined as meeting one of the following criteria:
  - Bulkiest sites of disease ≥2cm
  - Disease involving hip, shoulder or sacroiliac joints
  - Disease in long bones with 1/3-2/3 cortical thickness
  - Disease in junctional spine (C7-T1, T12-L1, L5-S1) and/or disease with posterior element involvement

Page **6** of **30** Version: 2/26/16

# 2.0 OBJECTIVES AND SCIENTIFIC AIMS

# **Primary Objective:**

 To assess whether early palliative radiation of the highest risk asymptomatic or minimally symptomatic bone metastasis in patients with metastatic cancer can decrease the number of SREs, defined as pathological fractures, spinal cord compression, or palliative radiotherapy and orthopedic surgery to bone.

# **Secondary Objectives:**

- To compare the number of hospitalizations related to SREs between standard of care and upfront RT arms
- To compare pain-related quality of life of between standard of care and RT arms, using the Brief Pain Inventory (BPI form
- To collect health care utilities in the standard of care and RT arms using the EuroQol Group EQ-5D-5L form
- To compare pain-free survival (PFS) and overall survival (OS) between RT and standard of care arms.
- To evaluate CTCAE v4 toxicity events in the upfront RT arms.

## 3.0 BACKGROUND AND RATIONALE

#### Radiation Therapy for Treatment of Bone Metastases

Patients with metastatic cancer are living longer due to advances in therapy. Bone metastases are a common manifestation for distant relapse for many solid tumors, and it is the third most common organ affected by metastases . Bone metastases represent a prominent source of cancer related morbidity. A metastatic bone lesion can impair function and decrease quality of life due to acute or chronic pain. It can also cause pathologic fracture and spinal cord compression. These skeletal-related events (SREs) are frequently addressed with palliative radiation therapy (RT) as it is an extremely effective palliative treatment for bone metastases. The current standard of care in patients with multiple bone metastases is to continue systemic therapy or observation, and patients are referred for consideration of palliative RT when the metastases become symptomatic. In the recently published American Society of Therapeutic Radiation Oncology consensus guideline, use of palliative radiation therapy in the treatment of painful bone metastases demonstrated a response rate of 70-80% in pain control across multiple studies. For the treatment of spinal cord compression, prospective trial also demonstrated a response rate of 90% 3 months after RT.

Page **7** of **30** Version: 2/26/16

# Rational to Study Timing of Radiation

Early palliative care has been shown to improve the quality of life and even survival for patients with metastatic cancer. More and more supportive oncology teams in cancer centers now advocate for early integration of radiation therapy in a patient's palliative management course. While multiple randomized studies have evaluated the efficacy of different radiation therapy regimens in the treatment of symptomatic bone lesions, there has not been a study that examined the impact of early, upfront radiation for asymptomatic or minimally symptomatic (non-opioid dependent) bone metastases and its efficacy in preventing SREs.

To better understand the pattern of inpatient radiation oncology care, an institutional inpatient radiation oncology consult registry was created which demonstrated that 319 of the 1,151 inpatient consults requested between July 2015 and June 2016 were for evaluation of symptomatic bone metastases in patients who were hospitalized for acute or chronic pain. Among these patients, two-thirds went on to receive RT for pain management. The most common sites treated with RT were spine (50%), joints such as hip and shoulder (11%), and long bones such as femur and humerus (11%). The median survival of all patients who were evaluated was 4 months, and 9% percent of patients discontinued RT to transition to hospice care, 8% died before the end of planned RT. Our data showed that in this selected patient population admitted for pain management of bone metastases, the overall prognosis is poor. Nevertheless, 61% of treated painful bone metastases were diagnosed at >4 months prior to RT. While RT is an effective treatment modality for palliation, it does appear RT may be delivered too late. The proposed trial seeks to understand whether it is beneficial to patients with metastatic disease to change the treatment paradigm to one of early, upfront RT prior to the development of symptomatic disease.

## Skeletal-Related Events as the Primary Endpoint

Skeletal-related events include fracture, spinal cord compression, and radiation or surgical interventions to bone such as for pain. SREs significantly impact health-related quality of life in patients with metastatic disease, and these events can also be distinctly measured and have been used as endpoints in clinical trials investigating therapies for bone metastases. Data from untreated arms of controlled trials of osteoclast inhibitors indicate that SREs ranged from 50-70% at 1-2 years, and treatment reduced the incidence to 38-50%. A phase III trial evaluating zoledronic acid in patients with metastatic prostate cancer or renal cell carcinoma demonstrated SRE rates of ~50% in patients with prostate cancer and ~90% in patients with metastatic renal cell carcinoma at 1 year. In another study, it was found that the baseline rate of SRE in patients with metastatic solid tumors with bone metastases was ~65% at 1 year, with the median time to SRE time being 155 days. Radiation therapy significantly reduces the risk of SREs in patients with symptomatic bone metastases. Nevertheless, no study to date has addressed the question whether RT to asymptomatic or minimally symptomatic highest risk bone

Page **8** of **30** Version: 2/26/16

metastases would significantly reduce risk of developing SREs in patients with bone metastases.

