## 5.2 Systemic Therapy

Standard of care systemic therapy, including chemotherapeutics, targeted therapies, immunomodulatory agents, and hormonal therapies will be delivered at the discretion of the treating medical oncologist. Patients may receive systemic therapy concurrently and there are no restrictions on initiation of systemic agents after radiotherapy including immunotherapy and hormonal therapy, the timing of which will be determined by a consensus between the treating medical and radiation oncologists.

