# 8.0 PRETREATMENT EVALUATION

The following tests must be completed prior to enrollment unless otherwise specified:

Prior to study entry (randomization):

patients approached (if applicable).

• Standard of care biopsy proving malignancy, with clinical documentation consistent with metastatic disease, per physician discretion.

Within 6 weeks (42 days) of study entry (randomization):

- CT CAP, FDG-PET/CT scan, MRI Total Spine or NaF-PET can be used, imaging study is at the discretion of the treating physician.
- Other local imaging studies that include the target lesion(s) can also be used as baseline imaging at the discretion of the treating physician.

Within 4 weeks (28 days) of study entry (randomization):

- CBC with differential
- Comprehensive metabolic panel (CMP=Na, K, Cl, CO2, BUN, Creatine, Ca, Glucose, total protein, albumin, alk phos, total bilirubin, AST and ALT).
- Complete medical history including current medications, comorbidities and performance status
- Physical exam including weight, height and vital signs (O2 saturation, blood pressure, heart rate, respiratory rate, and temperature).
- BPI short form and EQ-5D-5L
- Lesion Identification Worksheet should be completed by physicians

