## 14.0 BIOSTATISTICS

The primary objective of this study is to compare the rate of skeletal related events (SRE) from the date of randomization to death or 12 months, whichever occurs first, between patients who received standard of care versus upfront, early palliative RT to high-risk bone metastases. We expect 60-80% of the enrolled patients can be followed for 1 year. An SRE is defined as pathological fractures, spinal cord compression, or palliative radiotherapy and orthopedic surgery for bone pain. Data suggest that the event rate is around 60% in the standard of care arm . In our institutional experience, 75% of inpatient radiation consultation led to palliative radiation for painful bone

metastasis, an SRE. Furthermore, 61% of these lesions were diagnosed at least 4 months prior to undergoing RT. We believe 60% estimated event rate at 1-year is a conservative estimate.

The primary endpoint is a binary variable and the rate refers to proportion and is defined as the number of lesions that had SRE divided by the total number of target lesions. This analysis is lesion-based so an SRE (or no SRE) at one site does not affect the status of other sites from the same patient. We estimate that the investigational arm has the event rate around 30%. Radiation therapy is extremely effective in alleviating pain due to bone metastases with 70-80% pain control. By preventing the development of significant bone pain, which often leads to SREs, RT can effectively reduce SREs, To this end we will analyze at least 66 patients with valid SRE endpoint (randomized 1:1 to each arm) to achieve >80% power in detecting such a difference using a two-sample, one-sided proportion test with alpha<0.05. Since patients who withdraw before the endpoint can be evaluated will not be included in the analysis (i.e., it will NOT be an intent-to-treat analysis) we will over-accrue to account for withdrawals to ensure a minimum of 33 patients in each arm (subject to stratification, see Section 15.2) who can contribute the analyzable endpoint of SRE. We believe an additional 10% would be sufficient so totally we expect to randomize 74 patients. A small portion of patients (<15%) may have multiple lesions, in which case they will be treated as independent analysis units. In other words, the eventual effect sample size may be slightly higher than 66 because this objective will be analyzed per lesion.

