#### 15.2 Randomization

Patients will be randomized to the standard of care therapy arm or the early, upfront RT followed by standard of care therapy arm. For patients enrolled, immediately after consent is obtained, the CRC at MSKCC will register participants in the Clinical Trial Management System (CTMS). Once the participant's eligibility is established, the registration will be finalized and the participants will be randomized using the Clinical Research Database (CRDB). Randomization will be accomplished by the method of random permuted block, and will be stratified by disease histology and planned standard of care. After

Page **23** of **30** Version: 2/26/16

treatment arm is determined by randomization, the CRCs will notify physicians at MSKCC of the treatment arm within 24 hours of randomization. All data will be collected and analyzed at MSKCC.

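### The background reports fewer SREs with osteoclast inhibitors, but the plan neither adjusts for bone-modifying agents, says whether a stratum covers them, nor schedules a record of later use

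*Combined protocol and SAP*

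**What the plan says.** Section 3.0, under the heading on skeletal-related events as the primary endpoint, reports that "untreated arms of controlled trials of osteoclast inhibitors indicate that SREs ranged from 50-70% at 1-2 years, and treatment reduced the incidence to 38-50" per cent. It gives two ranges and no difference between them. The rates refer to 1-2 years and are not said to be per lesion.

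Outside the background and the reference list, no bone-modifying agent is named. The relevant places are:

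- **Section 5.2** describes "Standard of care systemic therapy, including chemotherapeutics, targeted therapies, immunomodulatory agents, and hormonal therapies" as given at the oncologist's choice. Sections 4.1 and 4.2 likewise leave standard therapy in both arms to the treating oncologist.
- **Section 8.0** collects at baseline a "Complete medical history including current medications, comorbidities and performance status".
- **Section 10.0** and its schedule list a history and physical, the BPI and other items at 3, 6 and 12 months. They contain no concomitant-medication item. The BPI asks only about treatment for pain.
- **Section 14.0** sets the primary comparison as lesions with an SRE divided by target lesions, within 12 months or until death, "in detecting such a difference using a two-sample, one-sided proportion test with alpha<0.05". No covariate is mentioned.
- **Section 15.2** says that randomization "will be stratified by disease histology and planned standard of care". The levels of the second factor are not defined.

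**The concern.** The plan's own background identifies a drug class that is associated with the primary endpoint. No blinding is described and only one arm receives upfront RT, so whoever prescribes such an agent knows the patient's arm. Two things could then move the SRE contrast for reasons other than RT: a chance imbalance in use at baseline, and a difference between arms in starting or stopping an agent afterwards.

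Baseline use could be taken from the medication history, but the plan does not commit to using it. Later use has no planned data item, so a reader of the report could not tell whether co-intervention was similar in the two arms. The design has little reserve to absorb a shift, because its power is almost exactly 80% at a one-sided 5% level.

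**Working it through.** **Inputs from the documents.** Control rate: "Data suggest that the event rate is around 60% in the standard of care arm". RT-arm rate: "We estimate that the investigational arm has the event rate around 30" per cent. One-sided alpha 0.05, aim "to achieve >80% power", 33 evaluable patients per arm (Section 14.0). SRE ranges 50-70% and 38-50% (Section 3.0).

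**Assumptions, not in the documents.** Half the patients use an agent. Its effect e is 12 to 20 points, from pairing like ends of the two ranges (50 - 38 = 12; 70 - 50 = 20). Unpaired ends would allow anything from 50 - 50 = 0 to 70 - 38 = 32. One lesion per patient is used for simplicity.

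**1. The plan's own figure.** With p1 = 0.60, p2 = 0.30 and mean 0.45:

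- n per arm = [1.645 × √(2 × 0.45 × 0.55) + 0.842 × √(0.24 + 0.21)]² / 0.30² = 32.9, so 33 per arm and 66 in total.
- 66 / 0.90 = 73.3, so 74 randomized.
- Power at 33 per arm = Φ[(0.30 - 1.645 × 0.1225) / 0.1168] = 80.1%.

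The stated design reproduces.

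**2. Chance imbalance at baseline.**

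- SD of the arm difference in use = √(0.25 × 2/33) = 0.123.
- P(|difference| ≥ 0.20) = 2 × [1 - Φ(0.20/0.123)] = 0.104.
- Shift from a 20-point imbalance = 0.20 × (0.12 to 0.20) = 2.4 to 4.0 points.
- With 30% or 70% use, the SD is 0.113 and the 95% limit of imbalance about 22 points (24 points at 50% use). The shift at that limit is 2.7 to 4.8 points across these cases.

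**3. Unequal use after randomization.** Suppose RT has no effect, the control rate is 60%, and use in the RT arm exceeds use in the control arm by d. The RT-arm rate is then 0.60 - d × e, and the chance of a significant result is Φ[(d × e - 1.645 × SE0) / SE1], where SE0 and SE1 are the pooled and unpooled standard errors.

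| d | e | RT-arm rate | False-positive rate |
|---|---|---|---|
| 0 | any | 60.0% | 5% |
| 0.20 | 0.12 | 57.6% | 7.4% |
| 0.20 | 0.20 | 56.0% | 9.4% |
| 0.30 | 0.12 | 56.4% | 8.9% |
| 0.30 | 0.20 | 54.0% | 12.4% |

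In the other direction, a true RT-arm rate of 30% with use 20 points higher in the control arm puts the control rate at 57.6% or 56.0%. Power falls from 80.1% to 74% or 69%.

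**4. What baseline adjustment gains.** At 50% use, a factor with effect e accounts for 0.25 × e² of the variance in each arm, that is 0.0036 to 0.0100. Removing it:

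- e = 0.12: Φ[(0.30 - 1.645 × √(2 × 0.2439/33)) / √(0.4428/33)] = 80.6%.
- e = 0.20: Φ[(0.30 - 1.645 × √(2 × 0.2375/33)) / √(0.4300/33)] = about 81.5%.

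The gain is at most about 1.5 points of power.

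**The case against.** **Balance.** A reader might infer that the trial leaves these agents unbalanced. The documents do not support that. Allocation is 1:1 and random, so a baseline imbalance arises only by chance, and the test's error rate already allows for it. The planned-standard-of-care stratum may cover these agents: the protocol summary describes Cohort 1 as receiving standard therapy for bone metastases, and the list in Section 5.2 is introduced as a set of examples. With the levels undefined, balancing is neither shown nor excluded. A stratum would in any case not govern what is started later.

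**Records.** A reader might also infer that use could never be known. That goes too far. Baseline medications are collected, a history and physical is scheduled at each visit, and this is a single-institution trial with source documents. What is missing is a dedicated item. Capture may be incomplete, because Section 10.0 allows telephone follow-up with the history deferred.

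**Effect size.** It is tempting to cite 12 to 20 points as the plan's own figure. The plan states no difference, and carrying 1-2 year trial rates over to lesions within 12 months is an assumption.

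**Later use as part of care.** Both arms are compared under discretionary care, so later use belongs to the strategies and is not automatically an error. Nothing in the documents suggests that prescribing will differ by arm, or in which direction. This stands, and it is why later use should be described and not adjusted away.

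**The planned test.** The primary analysis is a simple proportion test without a model, so adjustment changes the method that the sample size was based on. This also stands, and it is a reason to keep the unadjusted result in view.

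**Conclusion.** The concern holds as a modest gap in the analysis and data plan. A drug class that the background links to lower SRE incidence is not named as an adjustment factor, its place in the stratification is unstated, and no dedicated record of it is scheduled after randomization.

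On the assumptions of 50% use and a 12-20 point effect, chance imbalance is the smaller issue: about a 10% probability of 20 points or more, with a shift of 2.4 to 4 points at a 20-point imbalance. Unequal later use matters more. A 20-point difference favoring the RT arm would take the one-sided false-positive rate from 5% to about 7.4-9.4%. That difference is a scenario, not a forecast, since the documents give no figure for use in either arm.

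None of this shows that the primary comparison is biased. It shows that similarity of co-intervention could not readily be judged from the data as planned.

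**What to change.** 1. **Stratum.** State the levels of planned standard of care in Section 15.2, and whether bone-modifying agents are part of them.
2. **Baseline use.** Pre-specify use at randomization (yes/no, from the medication history in Section 8.0) as an adjustment factor for the SRE comparison. A Mantel-Haenszel stratified risk difference would serve, with a variance that allows for several lesions per patient, because agent use is shared by all of a patient's lesions. Report the unadjusted test beside it.
3. **Later use.** Record agent start and stop dates in both arms at 3, 6 and 12 months, and tabulate them by arm next to the primary result. Present this as a description of co-intervention. Later use can itself depend on arm, so it should not enter the model as a covariate.

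The cost is one data field with its dates, a slightly more complex primary analysis, and a short amendment. The precision gain is small (power from 80.1% to about 80.6-81.5%). The main benefit is that readers can see whether the arms received similar co-treatment. No rule on when such agents are given needs to change.

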# **Highest Risk Bone Metastases**

There is a paucity of data on the definition of highest risk bone metastases. However, based on the retrospective data from our institution, the most commonly treated bone metastases in inpatients for pain were in the spine (51%), joints such as hip and shoulder (11%) and long bones such as femur and humerus (11%). Thus, we propose to define the highest risk lesions as: 1. bulkiest sites of osseous disease ≥ 2cm, 2. disease involving the hip (acetabulum, femoral head, femoral neck), shoulder (acromion, glenoid, humeral head), or sacroiliac joints 3. Disease in long bones with1/3-2/3 cortical thickness (humerus, radius, ulna, clavicle, femur, tibia, fibula, metacarpus, phalanges) 4. Disease in junctional spine (C7-T1, T12-L1, L5-S1) and/or disease with posterior element involvement. Disease in the tibia or femur measuring > 2/3 cortical thickness is by Mirel's criteria at high-risk for a pathological fracture and should be treated surgically.

The use of preventative radiation in treating asymptomatic bone lesions is accepted, and has been documented in the literature. In 2010, Harada et al. evaluated 72 patients with 84 femoral lesions who received palliative radiation therapy. Of the 72 patients, 66 patients had symptomatic metastases and 7 patients had asymptomatic metastases. The radiographic response after radiation was 42% 3 months after radiation and was not found to be associated with pain relief, suggesting that radiation is effective in treating symptomatic and asymptomatic lesions. While radiation is frequently used to prevent bone metastases related complications from both symptomatic and asymptomatic bone lesions, the decision on whether radiation should be used for an asymptomatic bone lesion is extremely subjective as there has not been any prospective trial. We hope this study will allow us to gain knowledge on when radiation should be used to prevent SREs for future consensus.

